	The following null hypothesis will be tested:
	H _{0,prim} : p _T = 70%
	If $p_T > 70\%$ and the null hypothesis is rejected by a two sided, one sample χ^2 -test at 0.05 level, superiority will be concluded.
	Secondary objectives:
	The reference product will be tested in the same way.
	Regarding difference of cure rates of test and reference product p_T - p_R , the superiority of p_T vs p_R will be tested by following null hypothesis:
	H _{0,sup} : p _T - p _R =0.
	According ICH guideline "Points to consider on switching between superiority and non-inferiority" it is allowed to assess non-inferiority in addition to superiority if superiority cannot be shown. A non-inferiority margin has to be predefined. Moreover, no correction in terms of multiplicity is necessary. As non-inferiority margin δ , a 7.5% worse cure

	rate will be regarded as clinically not relevant.
	The following null-hypothesis will be tested on α -level of 0.025.
	$H_{0,NI}$: p_T - $p_R < \delta$, whereby $\delta = -7.5\%$
	The lower, one sided 97.5% confidence interval of difference p_T - p_R will be used for the test. If $H_{0,NI}$ will be rejected, non-inferiority will be shown.
	The difference of cure rates p_T - p_R as well the cure rates p_T and p_R will be presented with two sided 95% confidence interval.
	The other objectives will be investigated exploratory by descriptive statistics as well as by appropriate statistical tests.
	Details analysis and will be fixed in a detailed Statistical Analysis Plan (SAP).
Planned start of study	September 2014

3 Flow chart

Procedure	Scre	ening V V01	/isit	Evaluation Visit V02	Second Treatment Visit V03	Follow-up Visit V04
Study day	Day 0			Day 1 (±3h)	Day 7 (+1d)	Day 10 (-1d; +2d)
	-2h	0h	+1h	24h after end of administration (±3h)		
Informed consent process	•					
Case history incl. medical history	•					
Demographic (ethnic group, gender, age, hair length, body weight, height etc.)	•					
Checks for concomitant medication	•			•	•	•
Physical examination of the scalp to verify head lice infestation by study staff	٠					
Pregnancy test in urine ^A	•					
Inclusion/Exclusion criteria check	•					
Randomisation		•				
Skin irritation (baseline- assessment, pre-treatment): secondary infection, erythema, excoriation by blinded study staff ^B		•			•	
Eyes irritation assessment (baseline-assessment, pre- treatment) by blinded study staff ^B		•			•	
Administration of the investigational product by un- blinded study staff ^C		•			•	

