10.2 Secondary objectives

Secondary objectives refer to comparison of the cure rate of test product **GOLDGEIST**[®] FORTE using the following endpoints:

Secondary endpoint: Difference of cure rates (as defined as primary endpoints).

Secondary efficacy objectives:

- 2. To show that the cure rate at the end of day 10 (corrected for re-infestation) for the reference product GOLDGEIST[®] FORTE for all baseline infestations is better than 70%
- 3. To show that the test product **Exercise** has a cure rate superior to that of the reference product GOLDGEIST[®] FORTE

4. In case that superiority cannot be shown: to show that the test product **Exercise** is non-inferior to reference product GOLDGEIST[®] FORTE regarding cure rate. Thereby a non-inferiority margin of 7.5% will be used.

Further secondary objectives refer to objectives 3-4, however evaluated in subgroups or other time points.

- 5. Efficacy of the investigational products for head lice for mild and moderate baseline infestations (cure rate at the end of the study day 10, corrected for re-infestation)
- 6. Efficacy of the investigational products for head lice for all baseline infestation (cure rate at day 1)
- 7. Efficacy of the investigational products for head lice for mild and moderate baseline infestations (cure rate at day 1)

As further secondary objectives, safety and tolerability of test product **GOLDGEIST**[®] FORTE as well as the acceptance of the investigational products will be evaluated.

Secondary safety objectives:

- 8. To evaluate local tolerability by patient: subjective symptoms (burning, paraesthesia, pruritus): 0h, 1h, 24h, 7d and 10d p.a. (descriptive evaluation)
- 9. To evaluate global tolerability by the patient and study staff (number of subjects with global tolerability ratings of "very good", "good", "moderate", "poor", descriptive evaluation) at 10d after application
- 10. To evaluate skin irritation by study staff (secondary infection, erythema, excoriation) on day 0, 1, 7 and 10
- 11. To evaluate eye irritation by study staff on day 0, 1, 7 and 10
- 12. To evaluate characterisation of safety and tolerability of the investigational products considering Adverse Events in the study population

11 Study design

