This single-centre, randomised, controlled, investigator-blinded, comparative study will be conducted in 100 patients (female and male patients, \geq 1 year of age) with confirmed diagnosis of head lice infestation. The patients will be randomised in a 1:1 ratio on both treatment arms.

In this study a repeated treatment, as recommended in literature [20] will be performed. For twotreatment protocols it is recommended that the second treatment should be applied on day 7 to day 9 and the final assessment should be on day 10.

Both investigational products will be tested as given in the product leaflets in compliance with the above mentioned treatment recommendations.

Patients complying with the in- and exclusion criteria will receive the study medication according to a patient number, allocated in ascending order in correspondence with their inclusion into the study.

Treatment will be performed as described in chapter 15.4 (Administration of the investigational products). The member of the study staff who will administrate the treatment will be un-blinded because administration procedure, smell, consistency and colour of pediculicides differ. In any case, the member of the study staff performing the subsequent assessments (assessor) will be blinded.

After informed consent procedure, confirmation of the diagnosis, check of exclusion and inclusion criteria and randomisation the first administration of the investigational products will be performed by the study staff. At the next visit (24 hours p.a.) patients will be re-inspected for living lice, as well as for safety assessments.

On study day 7, after re-inspection for living lice the second administration with the same investigational product as in Visit 1 will be performed by the un-blinded study staff.

On study day 10 the final visit will be performed at the study centre for final assessments of tolerability and efficacy, performing the procedures listed in the general trial flow chart (see chapter 3). In case of a treatment failure or a re-infestation the patient will be referred to his/her practitioner.

12 Investigational products

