14.3 Method of assigning volunteers to treatment groups

This study will be randomised and investigator-blinded. When patients will arrive at the site they get a screening number. After the patient or his/her legal representative will give his/her written informed consent the patients will receive the subject number. Each patient who meets the inclusion and exclusion criteria will be assigned the lowest yet unassigned random number available at the centre. Randomisation will be performed during the Screening Visit V01 on day 0.

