15.2 Study Visits and measures

15.2.1 Screening Visit V01 (day 0): study initiation, registration, enrolment, randomisation, first administration

Patients with suspicion of head lice infestation will be recruited for this study. Written informed consent will be obtained from adult patients or the legal representative of minors. Children able to read and write have to give their assent in written. The assent of younger children will be given verbally as far as appropriate.

Patient's eligibility for participation in the trial will be established by the investigator prior to enrolment.

Demographic data (gender, subject age, hair length (short, shoulder long, mid-back, long), medical history, PTSS during the last week prior to the intended administration of the investigational products, concomitant diseases and concomitant medication (especially chronic medications and use of medications including OTCs during the last 1 weeks, and use of anti-head lice treatments) will be recorded.

Body weight and height will be determined.

The diagnosis head lice infestation will be confirmed by:

• identification of at least five living lice or nymph (immature forms) and five live eggs

The study staff will examine the entire scalp and head hair as described in 15.5.6. Every part of the hair will be examined and the findings will be documented in the CRF:

The severity of head lice infestation will be judged on a 4-point severity scale:

- 0 = no relevant infestation (0-4 lice and/or nymph present);
- 1 = mild (5-9 lice and/or nymphs present);
- 2 = moderate (10-24 lice and/or nymphs present);

• $3 = \text{severe} (\geq 25 \text{ lice and/or nymphs present}).$

Patients will be considered eligible for participation in the study if they do meet any of the inclusion and none of the exclusion criteria. Patients will be received a subject number in ascending order.

In order to ensure administration and precise efficacy and tolerability assessments the patients will be housed at the study site until the assessments 60 minutes after the end of administration have been finished.

The investigational products will be applied at the centre by un-blinded either physicians or specially-instructed nursing staff (see 15.4.

Date and times of start and end of application of the investigational product and times of tolerability and efficacy assessments will be documented.

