16.4 Analysis of secondary objectives

The reference product will be tested in the same way.

Regarding difference of cure rates of test and reference product p_T - p_R , following hypotheses will be tested:

Superiority p_T vs p_R:

 $H_{0,sup}: p_T - p_R = 0.$

If $p_T - p_R > 0\%$ and the null hypothesis is rejected by a two sided, two sample χ^2 -test at 0.05 level, superiority of test product will be concluded.

According ICH guideline "Points to consider on switching between superiority and non-inferiority" [23] it is allowed to assess non-inferiority in addition to superiority if superiority cannot be shown. A non-inferiority margin has to be predefined. Moreover, no correction in terms of multiplicity is necessary. As non-inferiority margin δ , a 7.5% worse cure rate will be regarded as clinically not relevant.

The following null-hypothesis will be tested on α -level of 0.025¹.

 $H_{0,NI}$: p_T - p_R < δ , whereby δ = -7.5%

The lower, one sided 97.5% confidence interval of difference p_T - p_R will be used for the test. If $H_{0,NI}$ will be rejected, non-inferiority will be shown.

The difference of cure rates p_T - p_R as well the cure rates p_T and p_R will be presented with two sided 95% confidence interval.

The confidence interval for the difference in cure rates is calculated by SAS procedure PROC FREQ using statistic option RISKDIFF.

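### The test-versus-reference comparison is valid but unadjusted for baseline infestation severity, so some precision and a pre-specified answer to chance imbalance may be given up

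*Protocol*

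**What the plan says.** Section 16.4 concludes superiority of the test product over the reference if the null hypothesis of equal cure rates is "rejected by a two sided, two sample χ^2 -test at 0.05 level". If superiority fails, non-inferiority is assessed: "The following null-hypothesis will be tested on α -level of 0.025", with the margin justified by the statement that "a 7.5% worse cure rate will be regarded as clinically not relevant". The interval that decides non-inferiority comes from this instruction: "The confidence interval for the difference in cure rates is calculated by SAS procedure PROC FREQ using statistic option RISKDIFF". Neither method names a stratum or covariate.

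Section 15.2.1 records severity at the screening visit: "The severity of head lice infestation will be judged on a 4-point severity scale". The classes are mild (5-9 lice or nymphs), moderate (10-24) and severe (25 or more). The lowest class (0-4) fails the entry criterion of five live lice, so every enrolled patient should fall into one of the other three. The flow chart in Section 3 places the scalp examination two hours before treatment, ahead of randomisation.

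Section 10.2 uses severity only to define a subgroup, in objectives 5 and 7: "Efficacy of the investigational products for head lice for mild and moderate baseline infestations". On allocation, Section 11 states "The patients will be randomised in a 1:1 ratio on both treatment arms", and Section 14.3 says that each eligible patient "will be assigned the lowest yet unassigned random number available at the centre". Stratification by severity is not mentioned.

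**The concern.** Severity by lice count is a clean pre-randomisation variable, and the protocol finds it relevant enough to define a subgroup by it. If heavier infestations are harder to clear, two things follow. A chance excess of severe cases in one arm moves the estimated difference in cure rates, and the named analysis takes no account of that excess. An interval that ignores a prognostic factor is also wider than it needs to be.

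The comparison is labelled secondary, but Section 9 gives the purpose of the study as showing efficacy and safety against a licensed product as a precondition for reimbursement. If a visible imbalance arose, an adjustment chosen after seeing the data would be hard to defend.

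**Working it through.** **Inputs from the protocol.** Two-sided 0.05 chi-square test for superiority; one-sided 0.025 and a 7.5-point margin for non-inferiority (Section 16.4); 42 evaluable per arm, inflated to 50 (Section 16.5). **Not in the protocol, so assumed:** the severity mix and the cure rate by class.

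**1. The plan's own figures.** All reproduce with unadjusted formulas.
- One-sample size, 90% against 70%: ((1.96·√0.21 + 1.282·√0.09)/0.20)² = 41.1, so 42. With 80% power it is 33.1, so 34.
- Inflation: 42 × 1.1 × 1.05 = 48.5, so 49, rounded to 50.
- Superiority at 42 per arm: 60% vs 90% gives 90.2%; 65% vs 90% gives 79.4%.
- Non-inferiority at 42 per arm, 70% vs 90%: standard error √((0.21+0.09)/42) = 0.0845; 0.275/0.0845 − 1.96 = 1.29, so 90.2%.

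**2. Large-sample effect of stratifying.** Let w be the class shares, T and R the class cure rates, d = T − R, and D the overall difference. Per patient in each arm:
- unadjusted variance: p_T(1−p_T) + p_R(1−p_R)
- stratified variance: Σw[T(1−T) + R(1−R)] + ½Σw(d−D)²

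Assumed mix mild/moderate/severe 30/40/30%, about 90% vs 65% overall, 50 per arm. Worked example, moderate gradient (test 97/91/82%, reference 83/65/47%): unadjusted 0.0892 + 0.2275 = 0.3167; stratified 0.2938 + 0.0033 = 0.2972; ratio 0.938, a 6% reduction. The 95% half-width goes from 1.96·√(0.3167/50) = 15.6 points to 15.1.

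**3. Simulation** (40,000 trials per scenario, same mix, 50 per arm). The finite-sample reduction is about 2 percentage points smaller than the large-sample one.

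| Gradient (test; reference) | Variance change, large-sample | Variance change, simulated | Superiority power, chi-square to CMH |
|---|---|---|---|
| None | 0% | +2% | 87.8% to 86.8% |
| Modest (95/90/85; 75/65/55) | −2% | 0% | 87.6% to 87.2% |
| Moderate (97/91/82; 83/65/47) | −6% | −4% | 88.2% to 89.1% |
| Very steep (100/94/75; 95/70/28) | −21% | −19% | 87.7% to 93.4% |

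At 42 per arm with no gradient, power goes from 81.4% to 79.8%.

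A further case uses 43 per arm (50/(1.1 × 1.05) = 43.3), mix 40/40/20%, test 97/90/76% and reference 85/70/40% (90% vs 70% overall). Variance falls about 8%. Superiority power goes from 67% to about 69% with the Cochran-Mantel-Haenszel (CMH) test, or about 71% if judged by the Mantel-Haenszel interval. Non-inferiority power goes from 91% to 93%.

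**4. Non-inferiority at equal rates (90% vs 90%).** Simulated power, unadjusted to stratified:
- 42 per arm: 22.1% to 23.4% (modest) or 25.3% (very steep)
- 50 per arm: 25.2% to 26.3% (modest), 24.9% to 28.0% (very steep)

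For 90% power the size needed is (1.96 + 1.282)² × 0.18/0.075², about 337 per arm.

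**5. Chance imbalance at 50 per arm.** With 30% severe, the standard deviation of the between-arm difference in that share is √(2 × 0.3 × 0.7/50) = 9.2 points. A gap of 10 points or more occurs in 26-34% of trials (20-33% severe), and of 15 points or more in about 10% (30% severe). With an assumed 20-point cure gap between severe and other patients, a 15-point imbalance shifts the difference by 0.15 × 20 = 3 points, which is 40% of the margin.

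**The case against.** Nothing in Section 16.4 is wrong. Under 1:1 randomisation the unadjusted test is valid, and its error rate already allows for chance imbalance in any covariate. The 3-point shift is ordinary sampling error within a half-width of about 12 to 16 points. The method also matches the sample size formulas. The arm comparison is secondary, and the one-sample test in Section 16.3 has no between-arm imbalance to adjust for. Analysis details are left to a SAP that is not shown, where a stratified supportive analysis may already sit. All of this stands, and it is why the point is minor.

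It does not remove the point. Section 16.4 names the test and interval outright, so this is a choice the protocol has made and not a detail it leaves open.

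Four stronger readings are tempting, and the documents do not support them:
- *That the comparison is biased or invalid.* It is neither.
- *That precision is certainly lost.* No section gives a severity mix or cure rates by class. Without a gradient, stratifying loses a little.
- *That the protocol declares severity prognostic.* Naming a subgroup shows interest in it, not how strongly it predicts cure.
- *That adjustment would repair a weak non-inferiority test.* Step 4 shows that sample size is the limit.

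**Conclusion.** The point holds in a limited form. The comparison of p_T and p_R is valid but leaves unused a baseline factor recorded in every patient, with no stratified allocation stated to offset that. Stratifying would change the variance of the difference by between about +2% (severity not prognostic, 1-2 points of superiority power lost) and about −20% (very steep gradient, nearly 6 points gained), with 0-8% lower over the modest to moderately steep range. These figures rest wholly on assumed mixes and gradients. The firmer benefit is having the handling of a severity imbalance fixed before the data are seen. The primary conclusion is unaffected. Priority is low.

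**What to change.** Before database lock, pre-specify for the comparison of p_T and p_R:
- a Cochran-Mantel-Haenszel test stratified by baseline severity class (mild, moderate, severe) for superiority;
- a Mantel-Haenszel common risk difference with its two-sided 95% interval, with the lower limit used for non-inferiority;
- a rule for merging adjacent classes when one is empty or sparse in an arm;
- the unadjusted chi-square test and risk difference kept as supportive results.

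If the sponsor prefers to keep the unadjusted analysis as the main one, the stratified version can be named as a sensitivity analysis, which still gives a pre-specified answer to imbalance. The cost is one paragraph of protocol or SAP wording and a few lines of code, with no new data. The downside is the small power loss shown above if severity turns out not to predict cure.

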16.5 Determination of sample size

The design of the trial including the number of subjects is adapted from a previous trial performed with Silcap shampoo [24] and based on statistical calculation.

According to [21], a 90% cure rate can be expected for the study medication. In general, a cure rate of 70% can be assumed to a minimal accepted cure rate. The primary objective refers to superiority of cure rate vs. this limit. A sample size of 42 is required for a one group χ^2 -test comparing cure rate of 90% with a fixed limit of 70% (two sided test; alpha-level of 0,05; power=90%; software nQuery advisor 7.0; power=80%: sample size=34).

For the reference group, the identical sample size is used. Assuming 10% drop outs and a 5% rate for re-infestation, the sample size has to be multiplied by 1.1×1.05 leading to approximately 50 cases (exactly: 49 cases which have been rounded up to 50 cases).

The sample size is also applicable to show secondary objectives 3 and 4, if following cure rates are assumed:

Superiority: 60% vs 90% (90% power), 65% vs. 90% (80% power).

Non inferiority (margin: -7,5%): 70% vs. 90% (90% power).

¹ For practical considerations: Note that the half width of one sided 0.025 one sided CI and two sided 0.05 two sided CI are equal.

16.6 Further statistical analyses

All variables will be tabulated and adequately described according to the respective data type (continuously scaled: mean, standard deviation, median, min, max; categorically scaled: counts and percentages). Results of appropriate statistical tests might be presented in addition. Details analysis and will be fixed in a detailed Statistical Analysis Plan (SAP).

16.7 Statistical software

SAS 9.2 or later versions will be used.

16.8 Quality control for statistical procedures

The statistical analysis will be conducted in compliance with the ICH E9 Note for Guidance on Statistical Principles for Clinical Trials (CPMP/ICH/363/96, 1998).

Quality control will be performed according to the SOPs of ACOMED statistik. Quality control includes checks of data, checks of calculations as well as formal checks of tables, listings and figures. All steps of quality control will be documented with signature of the reviewer and date of review.

17 Evaluation of efficacy parameters

The ITT population will be used for analysis of efficacy variables with exception of noninferiority, where PP population will be investigated.

The primary analysis will be repeated for PP population.

Missing values will not be imputed patients dropping out because of non-effective treatment will be counted as non-responders by study design.

Details of the analysis will be fixed in the Statistical Analysis Plan (SAP) which will be finalised before database lock.

18 Evaluation of safety parameter

For definition of safety set/population see section 16.1.

All analyses will be performed for the safety population. Due to the short treatment duration, the topical administration (associated with a low risk of systemic availability of pyrethrum or mineral oil) and comprehensive data on the safety profile of the active substance, laboratory safety tests will not be performed routinely.

Secondary parameters for tolerability and safety:

Local tolerability assessment (subjective	Burning, paraesthesia, pruritus at day 0 (0h, 1h), day 1, day 7 (0h, 1h) and day 10 p.a.
symptoms)	Frequencies and percentages (related to number of patients with information) will be given for each symptom.
Global tolerability	Patients will assess the overall treatment tolerability at day 10 p.a.
assessment (patient):	Frequencies and percentages (related to number of patients with

	information) will be given for each score as well as for the combined score "very good" / "good".
Global tolerability assessment (study staff):	The investigator will assess the overall treatment tolerability at day 10 p.a.
	Frequencies and percentages (related to number of patients with information) will be given for each score as well as for the combined score "very good" / "good".
Skin irritation	Secondary infection, erythema, excoriation of the skin at -1h (baseline assessment), day 0 (0h, 1h), day 1, day 7 (pre-treatment, 0h, 1h) and day 10 p.a.
	Frequencies and percentages (related to number of patients with information) will be given for each symptom
Eyes irritation	Irritation/Redness of the eyes at -1h (baseline assessment), day 0 (0h, 1h), day 1, day 7 (pre-treatment, 0h, 1h) and day 10 p.a.
	Frequencies and percentages (related to number of patients with information) will be given for each symptom.
PTSS, Adverse Events:	Pre-treatment signs and symptoms and treatment emergent adverse events will be described by frequencies on WHO preferred term and system organ class level.

19 Evaluation patient reported outcomes

Secondary parameters:

Satisfaction with the	The patient will assess the satisfaction with the esthetical effects of
esthetical effect:	the anti-lice product after treatment and hair drying on day 0 and day 7 p.a.

Frequencies and percentages will be given for each question.

20 Quality assurance

Quality assurance includes all activities undertaken during and after a clinical study to verify and control quality. It embraces internal quality control by the staff itself and by independent second persons as well as monitoring and separate auditing activities. All activities will be performed according to written procedures of the CROs and the facilities involved.

At CardioSec all processes of planning, performance and evaluation are embedded in a comprehensive quality assurance system.

Monitoring of the study will be performed in accordance with the requirements of ICH-GCP.

The monitor is responsible for review of the written Informed Consent, for documentation of ethics committee and ministry of health approvals, for routine review of the CRFs throughout the study, for verifying adherence to the protocol, amendments, study specific SOPs and the completeness, consistency and accuracy of the data being entered on them. All demographic and safety parameters will be 100% verified by the monitor. Furthermore the monitor will review

the TMF at the study site, study drug storage at the visits and check the drug accountability at the close-out visit.

During the interim monitoring visit, the monitor will review the study drug administration, treatment compliance, and the performance of assessments and to determine whether all Adverse Events are appropriately reported within the time periods required by GCP, the protocol, the sponsor, and the German requirements.

The independent QAU of CardioSec GmbH will check the study protocol including informed consent form in order to ensure that these documents are in accordance with GCP standards. The integrated clinical study report will be reviewed by the QAU of CardioSec GmbH and released if methods, procedures and observations are described accurately and are in accordance with the protocol, if potential deviations from the protocol are described thoroughly, and if the integrated clinical study report plausibly reflects the results obtained from the clinical performance, the biometrical report and from the TMF.

Review of Independent Ethics Committee or Institutional Review Board or regulatory inspections (with direct access to source data) are permissible.

In the case of monitor visits or trial audits initiated by the sponsor or by regulatory authorities, the Principal Investigator grant the monitor/auditor access to all documents and source data related to the trial, including all subject files, in order to enable the monitor/auditor to verify all data entered onto the CRFs or any other trial documentation against any source data and documents, while maintaining adequate pseudonymity of the subjects and the confidentiality of the data.

21 Ethics

